4.6 Analysis Sets

The following analysis sets will be defined and used for the analyses:

- Enrolled Analysis Set: all patients enrolled in the study. There will be no safety or efficacy analysis performed on this set.
- Safety Analysis Set: all patients randomized in the study to whom study medication has been dispensed. The safety analysis will be based on the actual study treatment dispensed.
- The Full Analysis Set (FAS): all patients randomized. Study treatment groups are defined by the randomized study treatment rather than the actual study treatment dispensed.

Upon database release, protocol deviation and analysis set outputs will be produced and will be sent to ABIVAX for review. An analysis set classification meeting will be arranged to discuss the outputs and to decide which patients and/or patient data will be excluded from certain analyses. Decisions made regarding the exclusion of patients and/or patient data from analyses will be made prior to unblinding and will be documented and approved by ABIVAX.

A summary of the number and percentage of patients assigned to analysis sets will be provided by treatment group and overall, for all enrolled patient.

A by-patient listing of analysis population details will be provided. This listing will be presented by treatment group and will include center, patient identifier, inclusion/exclusion flag for each population, and reason for exclusion from each population.

4.7 Demographic and Other Baseline Characteristics

Descriptive statistics (see Section 4.2) for demographics and other baseline characteristics and disease/medical history will be presented for patients assigned to FAS. All descriptive summaries will be presented overall and by country for each treatment group. Unless otherwise specified, percentages (%) will be based on the number of patients assigned to FAS (within subgroup stratification level, where relevant) with data available.

Original measurements, recorded in non-SI units will be converted to SI units for summaries as indicated below and will be listed in original and SI units:

$$kg = lb \times 2.204$$

$$cm = in \times 2.54$$

Demographics will be summarized, including:

- Age (years)
- Derived age category (< 65, \geq 65 years)
- Sex
- Race (American Indian or Alaska Native, Asian, Black or African American, Native Hawaiian or Other Pacific Islander, White, Other/Specification)
- Ethnicity (Hispanic or Latino, Not Hispanic or Latino, Not Stated, Unknown)
- Other Baseline characteristics, as recorded in the Vital Signs - Height and Weight eCRF at Visit 1
 - Height (cm).
 - Weight (kg).
 - Body mass index (BMI) (kg/m^2).

Baseline disease characteristics will be summarized, including:

- SARS-CoV-2 Status
- Days since onset of symptoms
- Risk factors associated to SARS-CoV-2 infection:
 - Age \geq 65 years
 - Obesity defined as BMI \geq 30 kg/m^2
 - Recent history of uncontrolled High Blood Pressure

- Treated diabetes (type I or II)
- History of ischemic cardiovascular disease
- Number of concurrent risk factors
- SpO2 (Visit 1)
- WHO Ordinal Scale (Visit 1)

Medical history/current medical conditions will be presented by treatment group and overall by number (n) and percentage (%) of all patients assigned to FAS according to the Medical Dictionary for Regulatory Activities (MedDRA version 23.0 or higher) primary system organ class (SOC) and preferred term (PT), regardless of whether the status is reported as ongoing or not ongoing at Visit 1. Unless otherwise specified, SOCs will be sorted alphabetically and within each primary SOC, the PTs will be sorted by descending order of total frequency (across all treatment groups combined). In the event of PTs with equal total frequencies, the relevant PTs will be sorted alphabetically. The number (n) and percentage (%) of patients having at least one medical history/current medical condition and having at least one medical history/current medical condition in each primary SOC, and for each PT will be presented. Hence if a patient reported more than one medical history/current medical condition with the same PT, the medical history/current medical condition will be counted only once. Similarly, if a patient reported more than one medical history/current medical condition within the same primary SOC, the patient will be counted only once at the SOC level.

Medical history/current medical condition, start date of event and ongoing status (yes/no) of each medical history/current medical condition as pre-specified in the Medical history eCRF will be presented in the by-patient data listing.

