4. STUDY POPULATION

4.1. Number of Patients/Centers

Approximately 800 patients will take part in this study with a maximum number of patients of 1034 following the interim analysis. These patients will be enrolled in approximately 75 sites located in Europe and Latin America (i.e. France, Germany, Belgium, Italy, Spain, United Kingdom, Brazil, Mexico, Chile, Peru).

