5. STUDY ASSESSMENTS AND PROCEDURES

5.1. Study Flow Chart

A detailed study flow chart (with all assessments) is displayed hereafter.

	TREATMENT PERIOD						UN SCH. VISIT	FOLLOW-UP PERIOD							
	V1 ¹³	Remote Medical Monitoring of Outpatients to be done every 2 days between D0 and D14	V2	V3	V4	V5 - End of treatment		V6 - Safety follow-up	V7 – long-term Fup						
	D0		D7 for hosp. Patients/and potentially outpatients	D14	D21	D28		D48	3 months post last SD intake						
GENERAL															
Signed inform consent form collection	X														
Check of IN/EX Criteria	X														
Demographic data collection	X														
Medical History	X														
Current medications	X	X	X	X	X	X	X	X							
7-point Ordinal scale	X		X	X	X	X		X	X						
PHYSICAL EXAMS															
Physical Examination (including vital signs) ¹	X		X	X	X	X	X	X							
Oxymeter and patient diary dispensation/collection	X			X											
Remote monitoring of body temperature, SPO2 and Clinical Signs of COVID-19		Monitoring every 2 days between D2 and D14													
Outpatients mortality status ¹²									X (remote)						
Body Weight (kg) & Height (cm) measurements ²	X														
ECG ³	X		X	X	X	X	X	X							
ANALYSIS TO BE PERFORMED LOCALLY															
Blood Pregnancy test (WOCBP) ⁴	X							X							
Hematology + Biochemistry ⁵	X		X	X	X	X	X	X	X ¹⁰ (Hb only)						
BIOBANKING															
Plasma (CRP, Troponin I & T, D-Dimer ⁶)	X		X	X	X	X	X								
Immunophenotyping and cells activation markers ⁷	X			X		X	X								
Blood sample Cytokines ⁸	X			X		X	X								
Nasopharyngeal and blood samples for viral load assessment	X		X	X	X	X	X								
Samples for miRNA-124 (Blood PAXgene tube)	X		X			X									
Haemostasis function exploration	X		X	X	X	X	X								
IMAGING															
Chest CT-SCANS ⁹	(X)		For hospitalized patients only – to be performed at discharge												
RESPIRATORY FUNCTION EVALUATION¹⁰															
Medical Research Council Dyspnea scale	For hospitalized patients only – to be performed at discharge								X						
Spirometry	(For hospitalized patients only – to be performed at discharge)								(X)						
CMDC	(For hospitalized patients only – to be performed at discharge)								(X)						
TREATMENT ALLOCATION															
Randomization	X														
ABX464/placebo treatment dispensation ¹¹	X														
ABX464/placebo treatment accountability						X									
SAFETY															
Adverse Events recording	X	X	X	X	X	X	X	X							

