¹ **Physical examinations:** a complete physical examination will be performed at D0, at the End of treatment visit (EoT), and at D48. Only differences from baseline will be reported at every other visit

² **Body Weight and Height:** Body weight and height will be measured at D0 for BMI assessment.

³ **ECG:** A 12-Leads ECG will be performed at every on-site study visit.

⁴ **Blood pregnancy test:** Applicable to all women of childbearing potential at D0 and at D48. In order not to limit the patient enrollment a urine pregnancy test can be performed in addition if the blood test result is not available at the time of randomization.

⁵ **Hematology + Biochemistry:** samples to be taken at every on-site study visit (except D7 for outpatients if not possible) and analyzed locally.

⁶ **CRP, Troponin I & T and D-Dimer:** samples to be taken at every on-site study visit (except D7 for outpatients if not possible) and sent to central laboratory for biobanking purpose.

⁷ **Immunophenotyping and cells activation markers:** samples will be taken in selected sites and for approximately 100 patients.

⁸ **Blood sample Cytokines:** samples will be taken in all sites for all patients.

⁹ **Chest CT-scan:** procedure concerns hospitalized patients only (whenever the hospitalization occurs during the course of the study). Images taken at discharge (\pm 7 days) will be assessed locally, then collected and sent to a blinded central reader for descriptive analysis of the lesions. If available at D0, Baseline CT scans of hospitalized patients will be sent to Central Reader for comparison purpose.

¹⁰ **Respiratory function evaluation:** This evaluation will be performed only in patients who were hospitalized during the course of the study. For these patients the MRC Dyspnea assessment scale must be used at discharge and 3 months after last study drug intake. For sites having adequate facilities a PFT (FEV₁ and slow and forced Vital Capacity) and a Carbon Monoxide Diffusing Capacity (CMDC) evaluation will be performed at discharge and 3 months after last study drug intake (optional assessments). For this last test, a blood sample for hemoglobin assessment must be taken within 48hrs prior to the CMDC test.

¹¹ **ABX464/placebo treatment dispensation:** treatment dispensation will be allowed once all the selection criteria are confirmed, including laboratory assessments for patients' eligibility confirmation.

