6.2 Schedule of Assessments

Table 3 Schedule of Assessments

Study Period	Treatment						Unscheduled Visit	Follow-Up (FUP)	
	Visit 1 [13]	Remote Medical Monitoring of Outpatients to be done every 2 days between	Visit 2	Visit 3	Visit 4	Visit 5 (EoT)		Visit 6 Safety FUP	V7 – Long-term FUP
Visit	Day 0		D7 for hosp. Patients/and potentially outpatients	Day 14	Day 21	Day 28		Day 48	3 months post last SD intake
GENERAL									
Signed inform consent form collection	X								
Check of IN/EX Criteria	X								
Demographic data collection	X								
Medical History	X								
Current medications	X	X	X	X	X	X	X	X	
7-point Ordinal scale	X		X	X	X			X	X
PHYSICAL EXAMS									
Physical Examination (including vital signs) [1]	X		X	X	X	X	X	X	
Oxymeter and patient diary dispensation/collection	X			X					
Remote monitoring of body temperature, SPO2 and Clinical Signs of COVID-19		Monitoring every 2 days between D2 and D14							
Outpatients mortality status [12]									
Body Weight (kg) & Height (cm) measurements [2]	X								

Parexel International

ABIVAX

ABX464-401

Statistical Analysis Plan

Study Period	Treatment						Unscheduled Visit	Follow-Up (FUP)	
	Visit 1 [13]	Remote Medical Monitoring of Outpatients to be done every 2 days between	Visit 2	Visit 3	Visit 4	Visit 5 (EoT)		Visit 6 Safety FUP	V7 – Long-term FUP
Visit	Day 0		D7 for hosp. Patients/and potentially outpatients	Day 14	Day 21	Day 28		Day 48	3 months post last SD intake
ECG [3]	X		X	X	X	X	X	X	
ANALYSIS TO BE PERFORMED LOCALLY									
Blood Pregnancy test (WOCBP) [4]	X								
Hematology + Biochemistry [5]	X		X	X	X	X	X	X	X [10] (Hb only)
BIOBANKING									
Plasma (CRP, Troponin I & T, D-Dimer [6])	X		X	X	X	X	X		
Immunophenotyping and cells activation markers [7]	X			X		X	X		
Blood sample Cytokines [8]	X			X		X	X		
Nasopharyngeal and blood samples for viral load assessment	X		X	X	X	X	X		
Samples for miRNA-124 (Blood PAXgene tube)	X		X			X			
IMAGING									
Chest CT-SCANS [9]	X								
RESPIRATORY FUNCTION EVALUATION [10]									
Medical Research Council Dyspnea scale	For hospitalized patients only – to be performed at discharge							X	
Spirometry	(For hospitalized patients only – to be performed at discharge)							(X)	
CMDC	(For hospitalized patients only – to be performed at discharge)							(X)	
TREATMENT ALLOCATION									
Randomization	X								

TP-GDO-WW-016-08

CONFIDENTIAL

Project Document Version No. 5.0

Effective Date: 26 Nov 19

Related to: SOP-GDO-WW-019

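### The SAP's pound-to-kilogram formula is inverted: any weight recorded in pounds would be reported 4.86 times too large, though the documents do not show that any was

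*SAP*

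**What the plan says.** SAP section 4.7 (Demographic and Other Baseline Characteristics) states: "Original measurements, recorded in non-SI units will be converted to SI units for summaries as indicated below". The same sentence has the listings show both the original and the converted value. Two formulas follow directly: kg = lb × 2.204 and cm = in × 2.54.

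Other places that bear on the point:

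- Protocol section 5.1 (Study Flow Chart) names the item "Body Weight (kg) & Height (cm) measurements", and its footnote gives the purpose: "Body weight and height will be measured at D0 for BMI assessment". The schedule in SAP section 6.2 labels weight and height in the same units.
- The list of baseline characteristics in SAP section 4.7 gives height in cm, weight in kg and BMI as taken from the height and weight page of the eCRF. Its list of risk factors includes "Obesity defined as BMI" of 30 kg/m² or more, and the number of concurrent risk factors.
- SAP section 4.2.4 summarises continuous data by mean, SD, median, minimum and maximum. Section 4.7 asks for these summaries overall and by country within treatment group.
- Protocol section 4.1 on the sites: "These patients will be enrolled in approximately 75 sites located in Europe and Latin America".

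**The concern.** The height formula is right: an inch is 2.54 cm. The weight formula uses the reciprocal of the constant it needs. A kilogram is about 2.204 lb, so multiplying pounds by 2.204 moves the value away from kilograms.

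This is operative text. SAP version 5.0 dropped the efficacy analyses but kept demographics and baseline characteristics, so baseline weight is still a planned output, and the sentence above the formulas provides for non-SI entries. A programmer who followed the SAP would produce a wrong weight for each pound record, in the summary table and in the SI column of the listing. Because the minimum and maximum are reported, one such record would normally set the maximum weight and inflate the SD.

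**Working it through.** **Inputs**

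- Printed multiplier: 2.204 (SAP 4.7).
- True multiplier: 1 lb = 0.45359237 kg by definition.
- Planned arm sizes: 533 and 267 (SAP 3.1). The number actually randomized before termination is not given.
- Patient weights: none are given. The values below are assumptions, shown over a range.

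**Does the printed constant reproduce?** Not as a multiplier: the correct multiplier is 0.45359. It does as a divisor: 1/2.204 = 0.45372, within 0.03% of 0.45359. So the constant is the right one and the operation is wrong.

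**Overstatement factor.** 2.204 / 0.45359237 = 4.859, or 4.86.

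**Size for one record**

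| Recorded (assumed) | True weight | Printed rule (lb × 2.204) | Error |
|---|---|---|---|
| 132.3 lb | 60.0 kg | 291.5 kg | 231.5 kg |
| 150 lb | 68.0 kg | 330.6 kg | 262.6 kg |
| 176.4 lb | 80.0 kg | 388.7 kg | 308.7 kg |
| 220.5 lb | 100.0 kg | 485.9 kg | 385.9 kg |

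**Shift in a group mean from one 150 lb record.** Shift = error / n.

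- n = 533: 262.6/533 = 0.49 kg.
- n = 267: 262.6/267 = 0.98 kg.
- Country-by-arm cell of an assumed 20 to 50 patients: 262.6/20 = 13.1 kg to 262.6/50 = 5.3 kg.

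Over the assumed range of 60 to 100 kg, the shift is 231.5/533 = 0.43 to 385.9/533 = 0.72 kg in the larger arm, and 231.5/267 = 0.87 to 385.9/267 = 1.45 kg in the smaller.

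**BMI, only if it is derived from the converted weight.** BMI is proportional to weight, so it is inflated by the same factor. The true BMI that would be reported as 30 is 30/4.859 = 6.2. In practice every pound record would then be classed as obese. At an assumed 1.70 m and 70 kg, a true BMI of 24.2 becomes 117.7 kg/m². The SAP gives no BMI formula and lists BMI among items recorded in the eCRF, so this step is conditional.

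**Is it corrected elsewhere?** No. The only other unit conversion, Fahrenheit to Celsius in SAP 4.11.4, is correct and concerns temperature.

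**The case against.** The strongest reply is that the rule may never run. The protocol flow chart, the SAP schedule and the SAP's own list of baseline items all name kilograms, the sites are in regions where pounds would not be expected, and the conversion applies only to non-SI entries, none of which is shown to exist. That stands, and it is why the point is minor.

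A second reply is that an error this large would be seen. Original and SI values are listed together, and SAP section 4.1 requires outputs to be independently checked; 330.6 kg beside 150 lb is hard to miss. This makes an undetected error unlikely, but it does not mend the rule. A checker programming from the SAP would reproduce the same value, and putting it right would mean departing from the SAP.

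Third, the mean shifts rest on an assumed patient and on planned arm sizes that a trial stopped for futility may not have reached, and the BMI consequence adds a further condition. Both are fair, and these figures should be read as illustrations. The factor 4.86 depends on none of them.

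Finally, the multiplication sign could be an artefact of text extraction. That is unlikely, since the height formula on the next line reads correctly, but a glance at the SAP page settles it.

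**Conclusion.** The formula is wrong as printed. Any weight recorded in pounds and converted by it would be 4.86 times too large. That conclusion needs no assumption about the trial.

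The practical effect depends on whether any weight was entered in pounds, which the documents do not show. If none was, the effect is zero. If one was, the descriptive weight summary and listing for that patient's group are wrong, and BMI, the BMI ≥ 30 item and the risk-factor count follow only if they are derived from converted weight. Eligibility and stratification do not use the formula, and SAP version 5.0 contains no efficacy analysis that it could affect. Severity is minor; confidence is high.

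**What to change.** Replace the weight formula in SAP section 4.7 with kg = lb × 0.45359, or equivalently kg = lb / 2.2046. With that rule 150 lb converts to 150 × 0.45359 = 68.0 kg. Then check the derivation program and any output already produced, including those prepared for the DSMB, to confirm that the printed formula was not used. Where BMI or the BMI ≥ 30 item is derived from converted weight, use the corrected weight; elsewhere nothing changes.

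The cost is one line of text and one program check, with no effect on design or analysis. Protocol section 9 asks that SAP amendments be documented and signed before final database lock. The documents do not say whether lock has occurred; if it has, the correction can be recorded in the study report instead.

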4.8 Prior and Concomitant Medication

Prior and concomitant medications will be analysed using the SAF. Prior and concomitant medications will be coded using the World Health Organization-Drug Dictionary (WHO-DD) Version March 2020 or later and will be classified by Anatomical Therapeutic Chemical (ATC) categories.

Prior and concomitant medications will be summarized separately. The number (n) and percentage (%) of patients taking medications will be summarized by ATC classification and PT, by treatment group and overall. Medications will be presented alphabetically by anatomical main group (the 1st

level of the ATC code). Within each ATC Level 1, the PTs will be sorted by descending frequency of the total number of patients with at least one medication in each PT. In the event of PTs with equal total frequencies, the relevant PTs will be sorted alphabetically. The number (n) and percentage (%) of patients having at least one concomitant or post-treatment medication in each ATC Level 1 and PT will be presented. Hence if a patient reported more than one concomitant or post-treatment medication with the same PT, the concomitant or post-treatment medication will be counted only once. Similarly, if a patient reported more than one concomitant or post-treatment medication within the same primary ATC Level 1, the patient will be counted only once. The overall number (n) and percentage (%) of patients receiving at least one medication and receiving at least one medication in each level of summarization will be presented relative to the total number of patients in the SAF.

Prior and concomitant medications (ATC Level 1/PT/Name), dose, frequency and route, start/stop date as specified in the Prior and Concomitant Medication eCRF with medication category (Prior only, both Prior and Concomitant or Concomitant only) will be presented in the by-patient data listing for FAS. Prohibited medications (Appendix 6.1) will be flagged in listings, as appropriate.

Medications will be categorized as follows:

Medication start and stop dates will be compared to the date of first dose of study medication to allow medications to be classified as either Prior or Concomitant. Medications starting after the treatment completion/withdrawal date will be listed but will not be classified or summarized.

Medications that start and stop prior to the date of first dose of study medication will be classified as Prior. If a medication starts before the date of first dose of study medication and stops on or after the date of first dose of study medication, then the medication will be classified as Concomitant. Medications will be classified as Concomitant if they have a start date on or after the date of first dose of study medication.

If medication start and/or stop dates are missing or partial, the dates will be compared as far as possible with the date of first dose of study medication. Medications will be assumed to be Concomitant only, unless there is clear evidence (through comparison of partial dates) to suggest that the medication started prior to the first dose of study medication. If there is clear evidence to suggest that the medication started prior to the first dose of study medication, the medication will be assumed to be both Prior and Concomitant, unless there is clear evidence to suggest that the medication stopped

prior to the first dose of study medication. If there is clear evidence to suggest that the medication stopped prior to the first dose of study medication, the medication will be assumed to be Prior only.

4.9 Treatment Compliance

Descriptive statistics for treatment compliance will be presented for patients assigned to SAF. Descriptive summaries will be presented for each treatment group and overall. Summary statistics will be provided for the following derived variables from data recorded in Drug Accountability eCRF:

$$\text{Exposure duration (days)} = \min(\text{Date Returned}, \text{Date of Death}) - \text{Date Dispensed} + 1$$

$$\text{Compliance (\%)} = 100 \times \frac{(\text{Number of Tablets Dispensed} - \text{Number of Tablets Returned})}{\text{Exposure duration}}$$

By-patient listing of drug accountability data as recorded on eCRF with derived compliance data will be provided for SAF.

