5.2.1. Visit 1 – Day 0 (D0 / Baseline)

Patient with a PCR or Rapid Antigen tests diagnosis of COVID-19 will be informed about the general aspects of the study and will sign and date the informed consent form. Only when patient written informed consent has been collected may further study procedures be carried out.

The patient number will be allocated once the patient is created in the eCRF.

At baseline, the following assessments will be performed:

- All inclusion/exclusion criteria will be verified,
- Collection of the signed informed consent form,
- Demographic data collection: year of birth, gender and ethnicity,
- Medical history documentation including comorbidities or associated risks,
- Start date (Onset) of COVID-19 symptoms and contamination date if known,
- All current medications must be recorded and all changes must be documented during the course of the study,
- Complete physical examination,
- Vital signs, body weight and height measurement,
- Record a 12 leads ECG,
- Report the disease severity rating using the 7-point ordinal scale (i.e. Not hospitalized, no limitations on activities; Not hospitalized, limitation on activities; Hospitalized, not requiring supplemental oxygen; Hospitalized, requiring supplemental oxygen; Hospitalized, on non-invasive ventilation or high flow oxygen devices; Hospitalized, on invasive mechanical ventilation or ECMO; Death);
- Supply outpatients with oximeter, and explain purpose and how to use it
- Collect samples for
 - Analysis performed by local lab: Hematology, biochemistry, serum pregnancy test for women of child-bearing potential (- an additional urine pregnancy test can be done if the result of the serum test is not available at the time of the study drug dispensation)
 - Biobanking purposes:
 - Viral load testing (nasopharyngeal and blood),
 - CRP, Troponin I & T and D-dimer,
 - Cytokines testing,

- Immunophenotyping and cells activation markers (samples will be taken in selected sites and for approximately 100 patients)
- Hemostasis function exploration
- miRNA124 assessment (Blood PAXgene® tubes),
- Patient randomization,
- Dispensation of study treatment allocated to the patient once all the selection criteria have been confirmed (including laboratory assessments for patients' eligibility)
- Administration of the first intake on site for safety purpose; Instruct the patient how to take the study drug once at home.
- Record all adverse event (if any) starting from the informed consent signature,

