- Immunophenotyping and cells activation markers (samples will be taken in selected sites and for the same patients as at Visit 1)
- Hemostasis function exploration
 - miRNA124 assessment (Blood PAXgene® tubes),
- Adverse Event and follow-up and reporting (if any),
- Collect the treatment kit dispensed at D0 for drug accountability and check patients' compliance,
- Schedule D48 visit.

After this visit, should a patient still need to be treated for COVID-19, the sites standard of care will be applied.

NB: At any visit, for hospitalized patients: collect chest CT scan at discharge (\pm 7 days) and send to central reader for analysis. In addition, an evaluation of dyspnea severity will be done at discharge using the Medical Research Council (MRC) dyspnea scale

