6.1. Description of investigational treatment

The study treatment that will be administrated to patients enrolled in this Phase 2/3 study consists of capsules containing ABX464 or its matching placebo given orally once daily with food for 28 days.

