6.3. Administration and dosing

6.3.1. Administration of the investigational product

Depending on the randomization, patients will be treated with a daily dose of 50mg of ABX464 or its matching placebo. All patients regardless of the treatment group will receive 1 capsule every day.

Patients will be orally dosed in a fed condition (e.g. regular breakfast or snack) with a glass of water.

Should a patient be intubated during the study, it's allowed to administer the study treatment through the feeding tube.

Should a patient be hospitalized during the course of the study, every effort should be made to ensure treatment compliance.

The minimum delay between 2 doses is 12 hours. Should a patient skip a dose s/he should take the next dose on the next morning.

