6.4. Method of assigning patients to treatment arms

All patients will be assigned a unique and incremental Patient Identification (ID) number. Patient IDs will be unique (i.e. reallocation of the ID will not be permitted). The format will be a seven-digit number as follows: site number (4 digits) – Patient number (3 digits). The latter 3-digit Patient number will be assigned according to the patient's order of inclusion in the center.

Eligible patients (i.e. those who fulfil all inclusion/exclusion criteria) will be randomized across the study according to a 2:1 ratio to ABX464 50mg : placebo treatment arms.

Patients will be stratified according to:

- Age \geq 65 years or $<$ 65 years (with at least one risk factor)
- Inpatient or outpatient, at the time of enrolment

Randomization will be performed via IWRS. Treatment numbers will be allocated as per randomization list.

In all cases at the end of treatment visit, all patient should return the bottle dispensed at D0 for a compliance check.

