7. STUDY COMPLETION

7.1. Patient Completion

Treatment with ABX464/Placebo shall continue until D28, except if a patient fulfils a premature discontinuation criterion (defined below).

Patients should be instructed to take their last study drug dose until the day before D28 visit. Should a patient start to take the treatment at D1, s/he will be instructed to take the last dose on D28.

After D28, patients will come back 21 days after the last study drug intake to perform an onsite safety follow-up visit at D48.

Following this visit, long-term follow-up for respiratory function exploration will be performed on-site for patients having been hospitalized during the study. This follow-up will take place 3 months after the last study drug intake.

For outpatients, a remote telephone follow-up will be performed 3 months after the last study drug intake.

Then, patients will exit the study and will be treated/follow-up according to the site standard of care.

Given the fact that the pulmonary function follow-up is exploratory and depends on the patient status during the study, a patient status is COMPLETE when the treatment period of 28 days is fulfilled, and the safety follow-up of 21 days is performed.

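### SAP 4.9 measures how long the bottle was out, not dosing: a patient who misses no dose scores 96.6%, and an early stopper's score depends on the return date

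*SAP*

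**What the plan says.** SAP 4.9 derives two variables from the Drug Accountability eCRF and summarises them on the Safety Set, by treatment group and overall. Exposure duration is "\min(\text{Date Returned}, \text{Date of Death}) - \text{Date Dispensed} + 1". Compliance is 100 × (units dispensed − units returned) / exposure duration. The current SAP contains no other definition of exposure.

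The protocol sets the calendar to which these formulas apply:

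- Start: study drug is dispensed at Visit 1, and the same visit includes "Administration of the first intake on site for safety purpose" (Protocol 5.2.1).
- Regimen: treatment is "given orally once daily with food for 28 days" (6.1), and "All patients regardless of the treatment group will receive 1 capsule every day" (6.3.1).
- Last dose: "Patients should be instructed to take their last study drug dose until the day before D28 visit" (7.1). For a later start, "Should a patient start to take the treatment at D1, s/he will be instructed to take the last dose on D28" (7.1).
- Return: the D28 visit in 5.2.5 includes "Collect the treatment kit dispensed at D0 for drug accountability", and 6.4 says "In all cases at the end of treatment visit, all patient should return the bottle dispensed at D0 for a compliance check".

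Separately, SAP 4.7 converts pounds to kilograms by multiplying by 2.204.

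**The concern.** Both ends of the exposure interval are logistics dates. For most patients the dispensing date is also the first-dose date, so the start does little harm. The end is the problem: death closes the interval, but stopping treatment does not, and it otherwise runs until the bottle is handed back. The variable therefore records custody of the bottle under the name of exposure, and it is also the compliance denominator.

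The SAP is now restricted to safety reporting, where exposure is basic context for the adverse event tables. If the printed exposure exceeds the days on drug, and the printed compliance falls short of actual adherence, a reader of the report gets the wrong picture of how the drug was taken. The Safety Set adds to this. SAP 4.6 admits patients by dispensing, whereas Protocol 9.1.2 requires at least one dose, so a patient who was dispensed drug and never took it would still receive a positive exposure.

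**Working it through.** The plan states no compliance or exposure figure, so there is nothing to reproduce; the check applies its formulas to its own calendar. Days use the protocol's numbering. The SAP's shift to Day 1 cancels, because only date differences enter.

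**1. Completer.** Dispensed D0, one capsule daily on D0 to D27, returned D28.

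- Capsules used: 28.
- Exposure under 4.9: 28 − 0 + 1 = 29 days. Days dosed: 27 − 0 + 1 = 28.
- Compliance under 4.9: 28/29 = 96.6%. On days dosed: 28/28 = 100%.

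**2. Visit window, D28 ± 2 days.** Dosing daily to the day before the visit:

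- Return on D26: 26/27 = 96.3%.
- Return on D30: 30/31 = 96.8%.

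A patient who takes exactly 28 doses and returns the bottle on D30 gets 28/31 = 90.3%.

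**3. Intake starting on D1.** Kit dispensed D0, doses D1 to D28, returned D28. Exposure is again 28 − 0 + 1 = 29, and compliance 28/29 = 96.6%.

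**4. Early stopper.** Seven doses on D0 to D6, none missed. With return on day r, exposure is r + 1 and compliance is 7/(r + 1). Every return date here is an assumption.

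| Bottle returned | Exposure under 4.9 (days) | Compliance under 4.9 |
|---|---|---|
| D6 | 7 | 100% |
| D7 | 8 | 87.5% |
| D14 | 15 | 46.7% |
| D21 | 22 | 31.8% |
| D27 (last intake D6 + 21 days) | 28 | 25.0% |
| D28 | 29 | 24.1% |

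Dosing is identical in every row: 6 − 0 + 1 = 7 days. With return on D27, exposure is 28/7 = 4 times the days dosed.

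**5. Weight formula in SAP 4.7.** For an illustrative 154 lb:

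- As printed: 154 × 2.204 = 339.4 kg.
- Correct: 154 / 2.2046 = 69.9 kg.
- Ratio: 339.4 / 69.9 = 4.86.

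**The case against.** The strongest reply is that little depends on these variables. They are descriptive. The capsule-count numerator is sound, the raw accountability data are listed, and Protocol 9.1.5 asks only for a count of daily doses. For completers the offset is one day and the same in both arms, so it does not distort the comparison between them. All of this stands, and it limits the point to the size given in the verdict.

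It can also be said that 25.0% for a seven-day patient is a reasonable figure, since 7/28 is compliance against the planned course. Days on treatment or days planned is indeed a reporting choice, and 100% is not the only defensible score. What cannot be defended is a denominator that moves with the return date: 4.9 gives 25.0% here only because the bottle happens to come back on D27.

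Several stronger readings are tempting, and the documents do not support them:

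- A reader might take 25.0% as what the plan would produce. Protocol 7.2 sets a visit 21 days after last intake but does not say the bottle is returned then. The flow chart places accountability only at the D28 visit.
- A reader might infer that adverse event rates, or the major deviation for fewer than 5 continuous days of treatment in SAP 4.5.2, inherit the error. The SAP does not tie either to 4.9.
- A reader might expect a D1 start to escape the offset. It does not when the kit is dispensed on D0, as step 3 shows.
- A reader might want the visit windows in SAP Table 2 changed too, because they also use the return date. For a completer the return day is the end-of-treatment visit day, so table and text agree. For early discontinuation, SAP 4.2.3 assigns the safety visit to Visit 6.

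**Conclusion.** The point holds, at modest size. As written, SAP 4.9 does not measure dosing. A completer who follows the protocol's calendar loses 3.4 percentage points (100 − 96.6) and gains one day of exposure, equally in both arms. The larger distortion is for early stoppers, where identical dosing can score anywhere from 100% to about 24% in the example, depending only on the return date. How many patients stopped early, when they returned the bottle, and whether this differed by arm are not in the documents, so the effect on the summary tables cannot be stated.

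The consequence is confined to the exposure and compliance summaries and the derived listing. No adverse event percentage or analysis set uses them.

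The pound formula in SAP 4.7 is a separate, minor error. It multiplies where it should divide, a 4.86-fold overstatement, but acts only on weights recorded in pounds. The protocol's flow chart schedules weight in kilograms, so it may touch nobody.

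**What to change.** In SAP 4.9:

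- Exposure duration = date of last dose − date of first dose + 1, and 0 if the patient was never dosed.
- Compliance = 100 × capsules taken / days a dose was due. State whether the denominator is days on treatment, the planned 28 days, or both; it must not depend on the return date. Showing both keeps early stopping visible.
- If no last-dose date is recorded, use the treatment completion or withdrawal date referred to in SAP 4.8, but only where it means last intake. A D28 visit date would bring back 28 − 0 + 1 = 29.

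Use the same duration for the treatment-duration item in the withdrawal listing of SAP 4.5.1, which is otherwise undefined.

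As a separate correction in SAP 4.7, write kg = lb / 2.2046.

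The cost is SAP wording, reprogramming of two derived variables and one conversion line. The SAP already relies on the first-dose date (4.3.1 and 4.8). The documents do not show whether last-dose date is a separate eCRF field, so this should be checked first.
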